MRT _{po}	Mean residence time of the analyte in the body after oral administration
██████████	██████████
NK	Natural killer
NOAEL	No observable adverse effect level
OCT2	Organic cation transporter 2
P-gp	P-glycoprotein
PK	Pharmacokinetic(s)
PKS	Pharmacokinetic set
PR	Pulse rate
QT	Time between start of the Q-wave and the end of the T-wave in an electrocardiogram
QTc	QT interval corrected for heart rate using the method of Fridericia (QTcF) or Bazett (QTcB)
RBC	Red blood cell
relative bioavailability	rel BA
REP	Residual Effect Period
SAE	Serious Adverse Event
SCR	Screening
SOP	Standard Operating Procedure
SRD	Single-rising dose
SYK	Spleen Tyrosine Kinase

Proprietary confidential information © 2020 Boehringer Ingelheim International GmbH or one or more of its affiliated companies

$t_{1/2}$	Terminal half-life of the analyte in plasma
T2	T type 2 inflammation
tid	three times a day
t_{\max}	Time from (last) dosing to the maximum measured concentration of the analyte in plasma
TMF	Trial Master File
TS	Treated set
TSAP	Trial Statistical Analysis Plan
TSH	Thyroid Stimulating Hormone
t_z	Time of last measurable concentration of the analyte in plasma
ULN	Upper limit of normal
V_z/F	Apparent volume of distribution during the terminal phase after extravascular administration
WBC	White blood cell
WHO	World Health Organization
WOCBP	Woman of childbearing potential
XTC	Ecstasy
ZAP70	Zeta-chain-associated protein kinase of 70 kDa
β	Slope parameter of linear regression line
λ_z	Terminal rate constant in plasma

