1.2.1.2 Clinical pharmacokinetics

In the 1371-0008 trial after each dose group, samples were analysed for BI 894416. A calculation of preliminary PK parameters was done based on planned sampling times; therefore PK parameters in the final Clinical Trial Report (CTR) might deviate. Preliminary PK parameters were assessed prior to each dose escalation to ensure that predicted gMean of

Proprietary confidential information © 2020 Boehringer Ingelheim International GmbH or one or more of its affiliated companies

C_{max} of patients did not exceed 5,233 nM, predicted gMean values for AUC_{0-24} did not exceed the maximum acceptable human exposure of 36,150 nM•h and that the upper limit of the 95% prediction interval for AUC_{0-24} of individual patients in the next dose group did not exceed 63,000 nM•h. Preliminary PK data from SRD part are shown in Table 1.2.1.2: 1 and from MRD part in Table 1.2.1.2: 2.

SRD part: AUC_{0-24} and C_{max} increased dose proportionally with increasing doses. At 170 mg the gMean exposure limit for C_{max} was met.

MRD part: trough values (data not shown) indicate that steady state was achieved after 4 days. After 7 days of tid. dosing, $C_{max,ss}$ as well as $AUC_{t,ss}$ increased with increasing dose and were well below the exposure limits described above.

Table 1.2.1.2: 1 Preliminary PK data from SRD part in 1371-0008

Dose group	N	AUC_{0-24} [nM•h/L]	C_{max} [nM]
75 mg qd	7	15200 (38.2)	2340 (29.7)
125 mg qd	7	25700 (29.9)	4128 (26.1)
170 mg qd	8	31700 (20.6)	5280 (24.3)

gMean (gCV%)

Table 1.2.1.2: 2 Preliminary PK data from MRD part in 1371-0008

Dose group	N	$AUC_{t,ss}$ [nM•h/L]	$AUC_{0-24,ss}^*$ [nM•h/L]	C_{max} [nM]
10 mg tid.	7	1470 (48.6)	4410	299 (42.7)
25 mg tid.	8	4800 (19.8)	14400	985 (19.4)
50 mg tid.	7	5400 (33.5)	16200	1290 (52.1)

gMean (gCV%)

* $AUC_{0-24,ss}$ is calculated with $AUC_{t,ss}$ to get the daily exposure for tid. dosing under steady state conditions.

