It is unknown whether BI 894416 or its metabolites are distributed into male semen. Therefore, there is a theoretical risk of a sub therapeutic exposure to BI 894416, or its metabolites, for a woman of child bearing potential (WOCBP) via the semen of a trial subject. Developmental and reproductive trials have not yet been conducted. Therefore, the effect of sub therapeutic concentrations of BI 894416, or its metabolites, with regards to embryofetal development has not been explored so far.

Risk mitigation: In order to address the risk of exposing an WOCBP to BI 894416, or its metabolites, via the subject's seminal fluid, subjects need to use barrier contraception (condom) or abstinence (see Section 3.3.3).

Phototoxicity

Phototoxicity potential of BI 894416 was measured in the open-lid Neutral Red Uptake test. There was no indication of phototoxicity by BI 894416. Subjects will be advised to avoid direct exposure to sun and UV light during the entire trial (see Section [4.2.2.2](#)). Further protective measures would not be necessary given the low phototoxic potential of BI 894416 (see IB [[c03536505](#)]).

Potential effects on QT interval

Preclinical trials suggested no proarrhythmic potential or cardiovascular liability with BI 894416. However, statistical results of first-in-man trial 1371-0001 suggested a dose- and concentration-dependent increase of QTcF interval. At gMean C_{max} of the 70 mg dose group, placebo- and baseline-corrected predicted mean QTcF increase was 5.9 ms (upper limit of the 90% confidence interval (CI) was 10.5 ms).

Risk mitigation: Subjects with cardiovascular disorders (Section [3.3.3](#), exclusion criterion 5), subjects who used drugs that cause QT/QTc prolongation (Section 3.3.3, exclusion criterion 11), subjects that show a marked baseline prolongation of QT/QTc interval or any other relevant ECG finding at screening (Section 3.3.3, exclusion criterion 20), and subjects with a history of additional risk factors for Torsade de Pointes arrhythmia (Section 3.3.3, exclusion criterion 21) are excluded from trial participation. Moreover, subjects will be in-house under close observation for 48 h following drug administration, and ECGs are done pre- and post-dose at the time points given in the [Flow Chart](#). Considering these risk-mitigating measures, the risks to subjects participating at trial 1371-0003 due to potential effects on QT interval are considered minimal.

Liver toxicity

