3. DESCRIPTION OF DESIGN AND TRIAL POPULATION

3.1 OVERALL TRIAL DESIGN AND PLAN

This single rising dose trial is designed as single-blind, randomised, and placebo-controlled within dose groups.

It is planned to include a total of 24 healthy male subjects in the trial. The subjects will be assigned to 3 groups consisting of 8 subjects per group; the groups will be dosed sequentially (see [Table 3.1: 1](#)).

The trial schedule and design is depicted in Figure 3.1: 1 and 3.1:2

[figure not shown]

Figure 3.1: 1 Overview of trial schedule

Figure 3.1: 2 Trial design

Within each dose group, 6 subjects will receive BI 894416 and 2 will receive placebo. Only one dose is tested within each dose group.

The dose groups to be evaluated are outlined in Table 3.1: 1 below.

Table 3.1: 1

Dose groups

Dose Group	1	2	3
Dose (mg)	25	50	70
Number of subjects	8	8	8
Subjects receiving placebo	2	2	2
Subjects receiving active drug	6	6	6

The groups will be dosed consecutively in ascending order of the doses, and a time interval of at least 7 d will be maintained between the last drug administration to subjects in the previous dose group (dose group N) and the first drug administration to subjects in the subsequent dose group (dose group N+1). The decision to treat the next dose group will be based upon safety and tolerability of all the preceding dose groups. The next dose group will only be treated if, in the opinion of the investigator (or authorised deputy, Sub Investigator), and Clinical trial leader (CTL), no safety concerns have arisen in the preceding dose groups, i.e. no dose-limiting events occurred, and if none of the pre-specified trial-specific stopping criteria have been met (refer to Section [3.3.4](#)).

A documented safety review must take place prior to each dose escalation. Furthermore, an unscheduled safety review meeting can be requested anytime for any reasonable cause by the Principal Investigator, or an authorised deputy, Sub Investigator, or the sponsor of the trial, e.g. in case of any unforeseen adverse events. Dose escalation will only be permitted if no safety concerns exist in the opinion of the Principal Investigator (or an authorised deputy, Sub Investigator) and the CTL.

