Although no formal Safety Review meeting will take place within a given dose group, safety will be continuously monitored during this trial, and an individual will only be dosed in the absence of any safety concern, i.e. no dose-limiting events occurred, and if none of the pre-specified trial-specific stopping criteria have been met (refer to Section 3.3.4).

At minimum, data from 4 subjects on active drug need to be available for escalation to a higher dose. The minimum data set for review consists of the following:

- AEs in the current and preceding dose groups up to at least 7 d post dosing including clinically relevant findings from ancillary safety testing listed below (Note: AEs may be ongoing at the time of Safety Reviews and AE information may be subject to change prior to Database Lock)
- Results from 12-lead ECG in the current and preceding dose groups up to at least 3 d post dosing
- Vital signs in the current and preceding dose groups up to at least 3 d post dosing.
- Clinical laboratory tests in the current and preceding dose groups up to at least 7 d post dosing
- Review of criteria for stopping subject treatment as per Section [3.3.4.1](#)

Proprietary confidential information © 2020 Boehringer Ingelheim International GmbH or one or more of its affiliated companies

The decision to escalate the dose will be made jointly by the Principal Investigator, or an authorised deputy, Sub Investigator, and the CTL after in-depth analysis of all available safety data, especially SAEs, AEs, and out-of-range laboratory results that are considered clinically significant by the investigator. Dose escalation will only be permitted if no safety concerns exist neither in the opinion of the Principal Investigator (or an authorised deputy, Sub Investigator) and the CTL.

Safety Reviews can be conducted face-to-face or by video/telephone conference. The CTL is responsible for the organisation and minutes of the reviews. Minutes will be signed off by the Principal Investigator (or an authorised deputy, Sub Investigator) and CTL, and will be filed in the investigator site file (ISF) and trial master file (TMF).

An overview of all relevant trial activities is provided in the [Flow Chart](#). For visit schedules and details of trial procedures at selected visits, refer to Sections [6.1](#) and [6.2](#), respectively.

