3.3.3 Exclusion criteria

Subjects will not be allowed to participate, if any of the following general criteria apply:

1. Any finding in the medical examination (including BP, PR or ECG) deviating from normal and assessed as clinically relevant by the investigator
2. Repeated measurement of systolic blood pressure outside the range of 90 to 140 mmHg, diastolic blood pressure outside the range of 50 to 90 mmHg, or pulse rate outside the range of 50 to 90 bpm
3. Any laboratory value outside the reference range that the investigator considers to be of clinical relevance
4. Any evidence of a concomitant disease assessed as clinically relevant by the investigator
5. Gastrointestinal, hepatic, renal, respiratory, cardiovascular, metabolic, immunological or hormonal disorders
6. Cholecystectomy or other surgery of the gastrointestinal tract that could interfere with the pharmacokinetics of the trial medication, except appendectomy or simple hernia repair
7. Diseases of the central nervous system, including but not limited to, any kind of seizures or stroke, and other relevant neurological or psychiatric disorders
8. History of relevant orthostatic hypotension, fainting spells, or blackouts
9. Chronic or relevant acute infections (Subjects who were positives to Hepatitis B surface antigen, Hepatitis B surface antibody, Hepatitis B core antibody, Hepatitis C antibodies, HIV-1 and HIV-2 antigen and/or antibody, T-SPOT and Syphilis test)
10. History of relevant allergy or hypersensitivity, including allergy to the trial medication or its excipients
11. Use of drugs within 30 d of planned administration of trial medication that might reasonably influence the results of the trial, including drugs that cause QT/QTC interval prolongation
12. Intake of an investigational drug in another clinical trial within 60 d of planned administration of investigational drug in the current trial, or concurrent participation in another clinical trial in which investigational drug is administered
13. Smoker, unless the subject quit smoking for at least 12 months prior to first planned administration of trial medication
14. Inability to refrain from smoking during trial
15. Alcohol abuse, i.e. consumption of more than 30 g per day
16. Drug abuse or positive drug screening

Proprietary confidential information © 2020 Boehringer Ingelheim International GmbH or one or more of its affiliated companies

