a) Central ECG lab

Central ECG lab evaluation will be performed (during the trial and/or after the trial) for first ECG of triplicate ECGs at every time point. For baseline, all three ECGs of the triplicate ECG at Day 1 pre-dose will be evaluated. This will include the determination of cardiac QRS-axis, as assessed by the ECG machine's algorithm, as well as the intervals RR, PR, QRS, and QT measured semi-automatically. Heart rate (HR) and the QT interval corrected for HR, i.e. QTcF and QTcB, will be determined by the sponsor (see trial statistical analysis plan [TSAP] for details).

All semi-automatic interval measurements in one subject will be performed on the same lead. The intervals will be measured from four cardiac cycles (beats) in lead II. If lead II shows a flat T wave, or is not measurable for any reason, lead V5 will be used. If lead V5 is not measurable, then lead I will be used. The lead actually used will be reported in the CTR. For automatic interval measurements no lead will be provided

For blinding arrangements see Section [4.1.5.1](#). No more than two blinded readers will evaluate all ECGs of the trial. ECGs from a particular subject should be evaluated by a single reader. For quality assurance and control of the measurements, all ECGs of a subject will be subsequently reviewed by the ECG technician's supervisor, or his/her designee, to assess the overall variance of the measured intervals, to detect accidental switching of leads and/or false subject assignments of the ECGs. After quality control, the fiducial point markings will be reviewed by the cardiologist assigned to the trial.

Evaluation of ECGs will comply with the ICH E14 guidance document and supplements [[R07-4722](#), [R16-0366](#)] as well as the FDA requirements for annotated digital ECGs [[R09-4830](#)].

b) Trial site

All local ECGs will be evaluated by the investigator or a designee.

For the inclusion, or exclusion, (see Section [3.3](#)) of a subject and for the assessment of cardiac safety during the trial, the QT and QTcB values generated by the computerised ECG system, or their manual corrections by the investigators, will be used. In doubtful cases, ECGs may be sent upfront, i.e. prior to the regular data transfer, for cardiologic assessment by the central lab. In this case, these centrally measured results would overrule any other results obtained.

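### No passage requires QTcF at an escalation review: in-trial cardiac safety rests on site QT and QTcB, although the known signal is in QTcF, so Section 3.1 should add an individual QTcF listing

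*Protocol*

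**What the plan says.** **Escalation review.** Protocol Section 3.1 states that "A documented safety review must take place prior to each dose escalation". The minimum data set includes "Results from 12-lead ECG in the current and preceding dose groups up to at least 3 d post dosing". It does not say whether site or central values are meant, and it names no correction formula. Data from 4 subjects on active drug are enough for a review.

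**Values used during the trial.** Under Section 5.2.4.1 b, for eligibility and for in-trial cardiac safety, "the QT and QTcB values generated by the computerised ECG system, or their manual corrections by the investigators, will be used". QTcF is not mentioned there.

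**Where QTcF comes from.** In Section 5.2.4.1 a, the sponsor determines QTcF and QTcB in connection with the central evaluation. On timing, that section allows the central work to be done during the trial, afterwards, or both, and Section 8.7 says the same. Doubtful ECGs may be sent early to the central lab (5.2.4.1 b), and Section 4.1.5.1 provides for an interim ECG safety analysis if one is required. Neither is scheduled.

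**The known signal.** Section 1.4.2 reports that results of trial 1371-0001 "suggested a dose- and concentration-dependent increase of QTcF interval". The predicted mean increase at the 70 mg gMean Cmax was 5.9 ms, with an upper 90% limit of 10.5 ms.

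**The stopping rule.** Section 3.3.4.3 stops escalation if at least 2 active subjects at one dose level have a QTc rise above 60 ms together with QT or QTc above 500 ms, confirmed by repeat ECG. The formula is not named, and the abbreviation list lets QTc mean Fridericia or Bazett.

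**The concern.** The sponsor knows of a QT effect and has described it in QTcF. The people who decide on escalation are directed to QT and QTcB. Bazett's formula divides by a higher power of RR than Fridericia's, so QTcB moves with heart rate even when QTcF does not. A subject whose heart rate falls after dosing can show too small a QTcB change, and one whose heart rate rises can show too large a change.

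What is at stake is the reading of individual subjects at the reviews after 25 mg and 50 mg, including whether a subject counts towards the QT stopping rule. That rule needs only 2 subjects, so the classification of one subject can matter.

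**Working it through.** **Plan's figure.** The 5.9 ms (upper limit 10.5 ms) comes from a model in another trial whose data are not in the documents, so it cannot be reproduced. It is used here only as stated.

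**Formulas** (RR = 60/HR in seconds):
- QTcB = QT / RR^(1/2)
- QTcF = QT / RR^(1/3)
- hence QTcB = QTcF × (HR/60)^(1/6)

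**Assumed inputs, not in the documents:** QTcF 400 ms and 60 bpm for the sensitivity; baseline QTcF 440 ms for the stopping-rule examples; heart-rate changes of up to 10 bpm. The heart-rate range comes from exclusion criterion 2, which excludes repeated "pulse rate outside the range of 50 to 90 bpm".

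**1. Sensitivity of QTcB to heart rate.** With QTcF fixed, the slope is QTcF × (HR/60)^(1/6) / (6 × HR). At 400 ms and 60 bpm this is 400/360 = 1.1 ms per bpm. It is 1.3 ms at 50 bpm and 0.8 ms at 90 bpm.

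| Heart-rate change from 60 bpm | QTcF change | QTcB change |
|---|---|---|
| −10 bpm | 0 | −12.0 ms |
| −5 bpm | 0 | −5.8 ms |
| +5 bpm | 0 | +5.4 ms |
| +10 bpm | 0 | +10.4 ms |

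**2. The stopping rule, read both ways, for one subject** (baseline 60 bpm, so QTcF = QTcB = 440 ms):
- *Masked.* QTcF rises to 505 ms (+65) and heart rate falls to 55 bpm. QTcB = 505 × (55/60)^(1/6) = 497.7 ms (+57.7), and QT = 505 × (60/55)^(1/3) = 519.9 ms. The absolute limb is met through QT on either scale. The limb for a rise above 60 ms is met in QTcF and missed in QTcB.
- *Inflated.* QTcF rises to 490 ms (+50) and heart rate rises to 70 bpm. QTcB = 490 × (70/60)^(1/6) = 502.8 ms (+62.8), and QT = 490 × (60/70)^(1/3) = 465.5 ms. QTcB meets both limbs and QTcF meets neither.

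These are constructed cases near the threshold. They show that the choice of formula can decide the classification, not that such cases are likely.

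**3. Size of the mean effect at the two reviews.** No escalation follows 70 mg. Assume the effect is linear in dose through zero: 5.9 × 25/70 = 2.1 ms and 5.9 × 50/70 = 4.2 ms. The only support for this quoted here is that AUC and Cmax "increased dose proportionally with increasing doses" in the single-dose part of trial 1371-0008, in patients at 75 to 170 mg. If the SD of the change is assumed to be 6 to 10 ms, the standard error for 6 active against 2 placebo subjects is SD × √(1/6 + 1/2) = 4.9 to 8.2 ms. That exceeds the effect, so a mean comparison at a review is uninformative on either scale.

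**4. Can the site produce QTcF?** Yes. A machine that prints QTcB has used an RR. Check: QT 380 ms at 72 bpm (RR 0.833 s) gives QTcB 416.3 ms and QTcF 403.8 ms. The QT and RR must belong to the same ECG after any correction. Suppose QT at 60 bpm is corrected by hand from 400 to 410 ms and the printed QTcB stays at 400. Combining the two as QT^(1/3) × QTcB^(2/3) then gives 403.3 ms, where the right value is 410 ms.

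**The case against.** Several arguments on the other side stand and limit the point.

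- **QTcF may be there anyway.** Central evaluation can run during the trial, doubtful ECGs can be read early, with the central result then overruling, and an ECG safety analysis can be called for. A reader might infer that the reviews would be held without QTcF. The documents show only that they could be.
- **Heart rate is not hidden.** Section 3.1 also puts vital signs to at least 3 d in the review data, pulse rate is one of them, and uncorrected QT is a site value. An alert reviewer could notice that QTcB moved with heart rate. ECGs are taken after at least 5 min supine rest, and no passage reports a drug effect on heart rate. Without a rate change, the two corrections nearly agree.
- **A small mean shift would not be found.** A reader might infer that a QTcF listing would reveal the 2 to 4 ms effect expected at 25 and 50 mg. Step 3 shows that it would not.
- **The late ECGs add little.** SAP Table 6.7: 1 gives no central evaluation at 34, 48 and 72 h, and a reader might infer that an important part of the window lacks central QTcF. With the longest gMean half-life in Section 1.2.2, 5.31 h, 34 h is 34/5.31 = 6.4 half-lives. About 1% of the drug remains, and a concentration-dependent 4.2 ms would be about 0.05 ms.
- **The doses are not new.** Healthy subjects have had 70 mg and patients 170 mg, and QT-related exclusions apply.

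What the objection does not remove is that none of the routes to QTcF is mandatory, and that the reviewers must do the rate correction by eye when it could be printed for them.

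**Conclusion.** The point holds at low severity. No passage requires QTcF before an escalation review. Section 5.2.4.1 b directs in-trial cardiac safety to site QT and QTcB, while the documented signal is in QTcF and the stopping rule leaves the formula open. At QTcF 400 ms, QTcB moves by 0.8 to 1.3 ms per bpm over 50 to 90 bpm with no change in QTcF. For a subject near the 60 ms limit, a shift of 5 to 10 bpm can change the reading in either direction.

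The figures rest on assumed baselines and heart-rate changes, since the documents give none. The value of a QTcF listing lies in individual-subject review, including a check of the stopping rule on QTcF. It does not lie in detecting a mean effect.

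A reader might also infer that a QT risk was overlooked in the trial as run. The documents do not support that: according to SAP Section 4, the trial stopped after 25 mg because of data from another study. This is a comment on the design.

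**What to change.** Add one item to the minimum data set in Protocol Section 3.1:

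*Individual QTcF and change from baseline by time point, calculated from site QT and RR of the same ECG (after any manual correction), shown beside QTcB and heart rate; central values where available.*

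Check the stopping rule in Section 3.3.4.3 on QTcF at each review, with the same thresholds. Site values remain in use for bedside safety, and central reading before a review remains optional.

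The cost is a small spreadsheet task per review. With one baseline, 11 time points to 24 h, and 34, 48 and 72 h, there are 15 values per subject, using the first ECG of each triplicate. That is 15 × 8 = 120 for a full group, or 15 × 4 = 60 for the permitted minimum of 4 active subjects. No extra ECG, central fee or longer gap between dose groups is needed. The one point of care is that any manual correction must be carried through to QT and RR together before QTcF is calculated.
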